5.4. Method of Assigning Subjects to Treatment Groups

Subjects will be assigned to a cohort based on the order in which they are enrolled. Subjects will be centrally randomized to treatment in a 6:2 ratio within each assigned cohort. The first 2 sentinel subjects will be assigned to treatment in a 1:1 ratio such that 1 subject receives KNX100 and the other receives placebo. Once eligibility is re-confirmed (Day -1), subjects will be randomized via a randomization list or an Interactive Web Response System. Of note, after Cohort 1, the CRC will determine the dose to be administered; therefore, randomization codes will only indicate whether the subject will receive active or placebo within their cohort.

Subjects will be sequentially assigned a Subject identification number upon signing the informed consent (i.e., site number 10, Screening number 001, 002 = Subject number 10-001, 10-002 etc.). Subjects will be identified by their Subject identification number throughout the study. Subjects will receive a 4-digit randomization number on Day 1 before dosing Replacement Subjects.

Subjects can be replaced. Replacement subjects will receive the same randomization number of the replaced subject +1000 (e.g., Subject 1111 will replace Subject 0111, Subject 1211 will replace Subject 0211, etc.). If more than one replacement becomes necessary, additional replacements will be numbered 2XXX, 3XXX, and so on (Table 5). The replacement subject will receive the treatment assigned to the withdrawn subject.

Table 5 Example 4-Digit Subject Randomization Numbers

Cohort	Original Subject Randomization Numbers	Replacement Subject Randomization Numbers
Part A		
Cohort 1	0111-0118	1111-1118, 2111-2118, 3111-3118, etc.
Cohort 2	0121-0128	1121-1128, 2121-2128, 3121-3128, etc.
Cohort 3	0131-0138	1131-1138, 2131-2138, 3131-3138, etc.
Cohort 4	0141-0148	1141-1148, 2141-2148, 3141-3148, etc.
Part B		
Cohort 1M	0211-0218	1211-1218, 2211-2218, 3211-3218, etc.
Cohort 2M	0221-0228	1221-1228, 2221-2228, 3221-3228, etc.
Cohort 3M	0231-0238	1231-1238, 2231-2238, 3231-3238, etc.

5.5. Blinding

The study will be performed in a double-blind fashion. The investigator and study staff (including lab personnel), the subjects, the monitors and the Sponsor's staff will remain blinded to the treatment until database lock.

The investigator will receive sealed envelopes with the individual randomization per subject to be opened in the case of emergency only.

The pharmacist of the site will receive the randomization list to enable packaging.

The randomization code will be kept strictly confidential by the pharmacist of the site. Double-blind conditions will be established so that the investigator, site personnel and subjects are blinded to the treatment assignments. Parameters to achieve and maintain the double-blind status of the study include:

- Sequential assignment of subject numbers within each cohort.
- Labeling of study drug with the study number.
- Packaging and delivery of study drug supplies to sites in a manner that maintains blinding.
- Matched appearance of study drug and placebo,

Subjects, investigators, and clinical staff will be blinded to therapy assignment. Sponsor representatives involved in the conduct of the study will be blinded to therapy assignment. The site pharmacy staff will be unblinded to study treatment.

To ensure study blinding, the active and placebo will be provided in identical capsules and an equivalent number of capsules will be administered to subjects receiving placebo (refer to [Section 5.3.2](#) and [Section 5.3.3](#)).

The following roles may be unblinded:

- Unblinded biostatistics team that prepares the randomization materials and handles treatment-revealing data prior to database lock.
- Selected study Sponsor personnel who are not directly involved in the conduct of the study.
- Pharmacy team.
- Drug-reconciliation clinical research associate (CRA).

A list of unblinded individuals will be maintained in study files. The pharmacy team will prepare the investigational product dispensing but will have no other role in the study and will not discuss any study-related observations with the blinded team members.

Analysis of the safety data for dose escalation decisions will be performed on blinded data and in a masked fashion. Analysis of PK parameters will be evaluated by members of the CRC. Please refer to [Section 9.8](#) for additional information.

5.6. Unblinding

The investigator and site personnel will remain blinded to the randomization code throughout the duration of the study. When necessary, code break envelopes will be available 24 hours a day, 7 days a week to unblind a treatment assignment.

Treatment assignment for an individual subject should be unblinded by the investigator only in an emergency, and only if knowledge of the treatment assignment is necessary for the clinical management or welfare of the subject. If possible, the investigator should contact the medical monitor before unblinding, but priority should be given to safety of the subject. The investigator must record the date and reason for unblinding.

Subjects may be unblinded in the event that an AE of Grade 3 or greater is reported in 2 or more subjects to support CRC data review and decisions regarding dose escalation or stopping criteria.

If deemed to be necessary, the CRC may be required to break the randomization code. Since the investigator is a member of the CRC, this will be performed by the investigator.

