3.2. Rationale for Study Design and Control Group

Study Design: This study is a 2-part, single site, single treatment, double-blind, randomized, placebo-controlled, dose escalating study to assess the safety, tolerability, and PK of single and multiple ascending doses and twice daily dosing of KNX100 administered orally to healthy males and females. Investigators and subjects will be blinded to treatment; however, the site pharmacist will be unblinded. Members of the CRC will be blinded; however, specific members may be unblinded to enable evaluation of PK and safety data for dose escalation decisions if required.

The design of this study is typical of those used for FIH studies with a "dose leader" (sentinel) design to better manage the safety aspects of the study. A sentinel design will be implemented during Part A, (SAD), with 2 subjects being dosed on the first dosing day of each Cohort. Of these, one will receive KNX100, and one will receive placebo. Safety and tolerability will be reviewed for these 2 sentinel subjects by the site, and CRC, before dosing the remaining subjects in the dose cohort.

All data for subjects in each SAD cohort collected up to and including the 30-hour samples postdose will be evaluated for safety and tolerability before opening the next higher dose cohort. In each MAD cohort, data for subjects up to and including the 24-hour timepoint post morning dose on Day 8 will be evaluated for safety and tolerability before opening the next higher dose cohort. The dosing schedule may be extended if additional observations are needed at a particular cohort. In the absence of unacceptable AEs, the CRC may decide to open the next

cohort before having reviewed data from all of the evaluable subjects who have completed Day 7 in the SAD cohorts and Day 14 in the MAD cohorts.

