5.3.1. Sentinel Subject Review and Toxicity Management

Part A Cohorts 1 through 4 will initiate dosing with 2 sentinel subjects who are randomly assigned so that 1 subject receives KNX100 and the other receives placebo. Following dosing of study medication, site personnel will observe the sentinel subjects for 48 hours, at which time the investigator will review the safety and tolerability for both sentinel subjects. This will include housing of the sentinel subjects in the Phase 1 unit for 30 hours postdose and then a follow up phone call at approximately 48 hours postdose administration.

Data reviewed will include AEs, clinical laboratory results, vital signs, and ECGs, EEGs, and PK parameters for both subjects. PK will be evaluated to ensure that exposure has not exceeded the maximum clinical exposure cap defined in [Section 6.20.1](#). Upon acceptance of reviewed data by the site and CRC, dosing may continue for the remaining 6 subjects. The investigator will document the review and decision by email to Sponsor representatives.

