9.8. Cohort Review Committee

An independent CRC will oversee the progress of this study and periodically review the accruing safety data. The CRC is intended to ensure that treatment does not pose undue risk to subjects.

The CRC will include an appropriate group of professional specialties, including at a minimum, the following core individuals:

- Blinded PI or delegate (delegation only when the PI is not available and must be a physician).
- Blinded medical monitor or delegate (must be a physician).
- Blinded neurologist with expertise in EEG analysis and interpretation.
- Blinded pharmacokineticist

The roles, responsibilities, constitution, and operations of the CRC (including its specific composition and schedule for its assessments) will be described in the CRC Plan, which will be reviewed and signed by each member before the first subject is randomized and treated.

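### The protocol has the blinded investigator who rates causality review PK for a one-active, one-placebo sentinel pair, and names that investigator to break the code if the CRC needs it

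*Protocol*

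**What the plan says.** **Blinding.** Protocol 5.5 keeps the investigator, site staff and sponsor staff blinded up to database lock and reserves the sealed envelopes for emergencies. Its list of roles that may be unblinded does not include the investigator, but does include the "Unblinded biostatistics team that prepares the randomization materials and handles treatment-revealing data prior to database lock". Section 5.6 adds: "The investigator and site personnel will remain blinded to the randomization code throughout the duration of the study". Section 9.8 lists the principal investigator as a blinded core member of the CRC, together with a "Blinded pharmacokineticist". Section 3.2 also calls the CRC blinded, but then says that "specific members may be unblinded to enable evaluation of PK and safety data for dose escalation decisions if required".

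**Sentinels.** Section 5.3.1 states: "Part A Cohorts 1 through 4 will initiate dosing with 2 sentinel subjects". Under 5.4 the pair is "assigned to treatment in a 1:1 ratio such that 1 subject receives KNX100 and the other receives placebo". Section 5.3.1 gives the 48-hour review to the investigator: "Data reviewed will include AEs, clinical laboratory results, vital signs, and ECGs, EEGs, and PK parameters for both subjects". Site and CRC must both accept the data before the other six subjects are dosed.

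**Code break for the CRC.** Section 5.6 allows for the CRC needing the code, if that is judged necessary, and continues: "Since the investigator is a member of the CRC, this will be performed by the investigator". SAP 3.2 repeats the CRC provision without saying who carries it out.

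**Who rates adverse events.** Protocol 6.17, 6.17.3 and 6.17.4 give severity and relatedness to the investigator. Section 8.5.1 lists related AEs and AEs by severity within the primary safety endpoint.

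**The concern.** KNX100 can be measured in the subject who took it and not in the one who took placebo. When a pair is known to hold one of each, PK results labelled by subject identify both. The person receiving them under 5.3.1 is the one who decides whether an AE is related to study drug. Section 5.6 then gives that person a second route to the assignments, outside the emergency use to which 5.5 restricts the envelopes.

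At stake is the value of the placebo comparison for the judged parts of the AE endpoint. A rater who knows that a subject took placebo has a reason to call an event unrelated. Relatedness also enters two escalation criteria in 5.3.4 and the first stopping rule in 6.20. The sections on blinding cannot all be followed as they stand.

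**Working it through.** The plan gives no figure on this point and makes no power calculation (Protocol 8.2), so there is nothing to reproduce. The check compares the sections and counts what the investigator could deduce.

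**1. Sections side by side.**
- Protocol 5.5 and 5.6: investigator blinded to database lock and throughout the study. Protocol 5.6: investigator breaks the code for the CRC if needed.
- Protocol 5.5: envelopes for emergencies only. A code break to support an escalation decision is not an emergency in the sense of 5.6, which ties that term to the clinical management or welfare of the subject.
- Protocol 9.8: all four core CRC members blinded. Protocol 3.2: some CRC members may be unblinded if required.
- Protocol 5.3.1: PK for both sentinels is in the review. Neither document describes dummy identifiers, a restricted reviewer, or a rule that causality be recorded before PK is seen.

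**2. Subjects exposed by the sentinel design.** Inputs: 4 Part A cohorts of 8, each 6 KNX100 and 2 placebo, each starting with a 1:1 pair.
- Sentinels: 4 × 2 = 8 of 4 × 8 = 32 SAD subjects, or 25%.
- Placebo sentinels: 4 × 1 = 4 of 4 × 2 = 8 SAD placebo subjects, or 50%.
- Against the 7 planned cohorts: 8 / (7 × 8) = 8/56 = 14.3%.
- Protocol 3.1 and SAP 3.1 mention sentinels only for Cohort 1. On that reading the count is 2 of 32, so 8 is an upper figure.

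**3. What can be deduced.** Possible assignments in a Part A cohort: 2 × C(6,1) = 12. With sentinel PK known by subject: C(6,1) = 6. Each sentinel's probability of being on active moves from 0.50 to 0 or 1. For the other six it stays at 5/6 = 83.3%, as fixed by design. Only PK for the whole cohort, unmasked by subject, takes the count to 1 (from C(8,2) = 28 in a Part B cohort). This assumes quantifiable KNX100 in the active sentinel; the documents give no assay limit.

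**4. Someone must separate active from placebo.** Protocol 5.3.4 compares mean KNX100 exposure with a cap, and below-limit values count as zero (8.7). If two placebo zeros were averaged in with six active subjects, the mean would be 6/8 = 0.75 of the active mean: an active mean of 113.2 ng/mL would read as 113.2 × 0.75 = 84.9 ng/mL, exactly the Cmax cap. The first stopping rule in 6.20 counts events only in subjects on active treatment. Need for assignments is therefore foreseeable, and no section says who supplies them for these checks.

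**5. How likely a code break is.** The one specific trigger in 5.6 for unblinding in support of the CRC is a Grade 3 or higher AE in 2 or more subjects. No event rate is given, so p = 1% to 10% per subject is an assumption, taken as equal and independent across subjects. Per cohort, P = 1 − (1 − p)^8 − 8p(1 − p)^7; for at least one of 7 cohorts, 1 − (1 − P)^7.

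| p | per cohort | any of 7 |
|---|---|---|
| 1% | 0.3% | 1.9% |
| 5% | 5.7% | 33.8% |
| 10% | 18.7% | 76.5% |

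Meeting the trigger permits unblinding but does not require it. The code break is a possible event, not a planned one.

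**The case against.** The case on the other side is substantial, and much of it stands as a limit on size.

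- **Cohort data are labelled blinded.** Protocol 5.3.4, 5.5 and 9.8.1 describe CRC data as blinded or masked. A reader might infer that by-subject cohort PK reveals all 56 planned subjects. The documents do not say that it reaches the investigator unmasked, so this is not established.
- **A team for such data exists.** Subject-level concentrations fit the treatment-revealing data that 5.5 gives to unblinded biostatistics, and the CRC Plan, which is not among the documents, may supply the masking. However, 5.3.1 makes no link to that team and puts PK for both subjects in the investigator's review.
- **The code break is conditional**, and events that meet the Grade 3 trigger have been graded before the break. Their causality can still be revised, and later events are rated with the assignment known.
- **Timing.** Under Protocol 6.17.2 a SAD treatment-emergent event starts within 24 hours of dosing, before the 48-hour review, so some ratings will precede PK. Nothing locks them. AEs are collected to the follow-up visit (Appendix 1), and the SAP 6.4.1 definition of treatment emergence has no 24-hour limit.
- **Much of the safety assessment does not use relatedness.** The non-tolerated-dose rule (6.20.2) counts Grade 3 or higher AEs whatever their cause. Emergent interictal discharges are suspected adverse reactions by rule (6.17.6), postdose EEGs are read by a specialist (6.20), and the exposure caps involve no rating. Laboratory results and overall TEAE incidence do not depend on causality.

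None of this removes the conflict between 5.3.1 and 5.6 on one side and 5.5, 5.6 and 9.8 on the other.

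**Conclusion.** The contradiction is real. Followed as written, 5.3.1 can disclose both sentinel assignments to the causality rater, and 5.6 makes that rater the code-breaker if the CRC asks. The exposure built into the design is up to 8 of 32 planned SAD subjects, including half of the SAD placebo group (4 of 8). This assumes sentinel pairs in all four SAD cohorts, PK seen by subject, and quantifiable drug in the active sentinel.

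A reader might go further and conclude that the double blind is lost for the whole study. The documents do not support that: disclosure beyond the sentinels depends on unmasked cohort PK or on a conditional code break. Nor do they support any figure for the resulting bias. Its size is unknown, and it can act only on the investigator-judged AE components, in a study that is descriptive and tests no hypothesis. The point merits correction because it bears on a primary endpoint component and on rules that use relatedness, and because correcting it is cheap.

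**What to change.** A cheap improvement, made in protocol and CRC Plan wording:

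- **5.6:** CRC-requested, non-emergency code breaks are done by the unblinded biostatistics team already listed in 5.5, not by the investigator.
- **5.3.1, 5.3.4 and 9.8:** subject-identifiable PK goes to that team, or to one named unblinded pharmacokineticist as 3.2 allows. That role checks individual exposure against the cap, which keeps the individual monitoring in 6.12.1. The investigator and other CRC members receive the cap result and PK under masked identifiers.
- **Order of recording:** severity and causality of events already reported are entered before any PK review or code break.
- **Consistency:** reconcile 3.2, 5.3.1, 5.5, 5.6 and 9.8, including whether the pharmacokineticist is blinded, and align SAP 3.2 and 3.4.

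Emergency unblinding and every escalation and stopping threshold stay as they are. The cost is one extra hand-off before each CRC review and less individual PK visible to the investigator. No new role is needed if the existing team is used, but the CRC Plan should state that it will be available when the CRC meets.

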5.7. Missed Doses

During Part A (SAD), study subjects will receive only 1 dose of product; therefore, missed doses will not be an issue.

During Part B (MAD), missed doses will be recorded in the electronic case report form (eCRF) along with the reason. During the MAD phase, missing 2 or more doses will constitute a protocol violation. Such study subjects may be replaced with due consideration of circumstances by the study CRC (refer to [Section 9.8](#)).

5.8. Overdose

An accidental overdose is highly unlikely because a licensed, unblinded pharmacist will dispense KNX100. In the event of an accidental overdose, the site shall contact the medical monitor immediately to discuss an appropriate course of action and follow-up.

5.9. Concomitant Therapy

All therapy ongoing at the time of enrollment and all therapy (other than study drug) received during the study is considered concomitant therapy for purposes of this study.

Intake of prescription or nonprescription is prohibited within 14 days or 5 half-lives of the drug, whichever is longer, prior to the first dose study medication, until completion of the follow-up visit.

Investigators may prescribe any concomitant medications or treatments deemed necessary to provide adequate supportive care. All concomitant medications taken during the study will be recorded with indication, dose information, and dates of administration.

Subjects cannot be enrolled if they have received prescription drugs or OTC medication including dietary supplements, standard dose vitamins, or herbal products within 14 days prior to the first administration (with the exception the oral contraceptive pill).

5.10. Restrictions

As this study is being conducted in healthy volunteers and, to date, no drug-drug interactions have been identified, no prohibited concomitant therapy has been defined.

5.10.1. Smoking

Subjects must be non-smokers or willing to abstain from smoking or using tobacco products from Day -1 throughout the entirety of the study.

5.10.2. Prior Therapy

Restrictions for prior therapy are as noted in [Section 4.3](#).

5.10.3. Fluid and Food Intake

While in the study clinic, subjects will not be allowed to consume any food and beverages not provided by the institution. Standardized meals will be provided for all study subjects.

During each dosing session, subjects will abstain from ingesting caffeine or xanthine-containing products (e.g., coffee, tea, cola drinks, and chocolate) for 10 hours before the start of morning dosing until after collection of the final PK and/or PD sample.

Use of alcohol will not be allowed from screening until after the EOS/ET visit.

Subjects should fast overnight prior to screening and for 2 hours prior to administration of a second dose of study drug (MAD Cohort 3). Subjects should avoid consumption of food for up to 2 hours following administration of all doses of study drug.

5.10.4. Exercise

Subjects must abstain from strenuous physical activity for 48 hours prior to admission until discharge on Day 2 (SAD) or Day 8 (MAD).

5.11. Treatment Compliance

Site personnel will administer study drug; therefore, treatment compliance is not a concern for this study.

5.12. Packaging and Labeling

All study treatments will be manufactured, packaged, and labeled under GMP conditions, and will be supplied to the clinical site pharmacy as unblinded study products. A certificate of analysis will be provided for each strength.

Study drug (KNX100 and placebo) will be encapsulated in hydroxypropyl methylcellulose (HPMC) dark green opaque size 0 capsules and packaged in 100 mL high density polyethylene (HDPE) Duma Twist-off bottles with polypropylene twist-off, 45 mm closures.

Each bottle will have a label that will contain, at a minimum, the protocol number, lot number, name and strength of the product, quantity of dosage units, directions for use, storage conditions, country-specific regulatory caution statement, and name and address of the Sponsor.

5.13. Storage and Accountability

All study drug must be kept in an appropriate, limited-access, secure place until it is used or returned to the Sponsor or designee for destruction. All Sponsor-supplied drugs must be stored under the conditions specified on the label and remain in the original container until dispensed.

Study drug should be stored at room temperature conditions (25°C [77°F]); with excursions permitted to 15°C-30°C [59°F-86°F], refer to USP Packaging and Storage Requirements).

Upon receipt of the study drug, the investigator or designee must verify the contents of the shipments against the packing list. The verifier should ensure that the quantity is correct, that the medication is received within the labeled storage conditions, and that the package is in good condition. If quantity and conditions are acceptable, the investigator or designee should acknowledge the receipt of the shipment. If there are any discrepancies between the packing list versus the actual product received, Kinosis must be contacted to resolve the issue. The packing list should be filed in the investigator's essential document file.

The site must maintain 100% accountability for all study drugs received and dispensed during the entire participation in the study. Proper drug accountability includes, but is not limited to:

- Frequently verifying that actual inventory matches documented inventory.
- Verifying that the log is completed for the drug lot (or ID or lot number) used to prepare each dose.

- Verifying that all containers used and unused are documented accurately on the log.
- Verifying that required fields are accurately completed and are legible.

The investigator should ensure that study drug is used only in accordance with the approved protocol. Study drug shall be dispensed only to subjects enrolled in the study. If any dispensing errors or discrepancies are discovered, the Sponsor must be notified immediately.

The site must record the current study inventory on a Sponsor-approved drug accountability log. At a minimum, the following information will be recorded for each subject:

- Protocol number and title.
- Name of investigator.
- Site identifier and number.
- Description of Sponsor-supplied drugs.
- Date and amount dispensed, including initials of the person dispensing the drug.
- Date and amount returned as unused including the initials of the person receiving the Sponsor-supplied drug.

The log should include a separate entry for each subject who receives Sponsor-supplied study drug.

Prior to site closure or at appropriate intervals, a representative from the Sponsor or its designee will perform study material accountability and reconciliation before study materials are returned to the Sponsor or its designee for destruction. The investigator will retain the original documentation regarding study material accountability and return of study materials; copies (as required) will be sent to the Sponsor or designee.

The investigator will be notified of any expiry date or retest date extension of study material during the study conduct. On expiry date notification from the Sponsor or designee, the site must complete all instructions outlined in the notification, including segregation of expired study material for return to the Sponsor or its designee for destruction.

